4.2 Study Population

4.2.1 Inclusion Criteria

1) Signed Written Informed Consent

- Before any study procedures are performed, subjects will have the details of the study described to them, and they will be given a written informed consent document to read. Then, if subjects consent to participate in the study, they will indicate that consent by signing and dating the informed consent document in the presence of study personnel. This informed consent will be scanned into the patient's EMR, as well as retained for a period not less than three years after the completion of the study.

2) Target Population

- Patients diagnosed with new-onset persistent or recurrent atrial fibrillation after isolated CABG surgery. Persistent atrial fibrillation is defined as an episode of >12 hours. Recurrent atrial fibrillation is defined as two or more episodes of atrial fibrillation lasting longer than 30 minutes.

3) Age and Reproductive Status

- Males and Females, at least 18 years of age
- Women of childbearing potential (WOCBP) must have a negative serum or urine pregnancy test (minimum sensitivity 25 IU/L or equivalent units of HCG) within 24 hours prior to the start of study drug. Patients undergoing isolated CABG must have this tested and documented prior to the procedure, and this will be verified prior to randomization.
- Women must not be breastfeeding.
- WOCBP must agree to follow instructions for method(s) of contraception for the duration of treatment with study drug(s): 30 days of treatment plus 5 half-lives of study drug Apixaban (3 days) or warfarin (8 days) plus 30 days (duration of ovulatory cycle) for a total of 38 days post-treatment completion.
- Males who are sexually active with WOCBP must agree to follow instructions for method(s) of contraception for the duration of treatment with study drug(s): 30

days of treatment plus 5 half-lives of study drug Apixaban (3 days) or warfarin (8 days) plus 90 days (duration of sperm turnover) for a total of 98 days post-treatment completion.

- Azoospermic males and WOCBP who are continuously not heterosexually active are exempt from contraceptive requirements. However they must still undergo pregnancy testing as described in this section.

Investigators shall counsel WOCBP and male subjects who are sexually active with WOCBP on the importance of pregnancy prevention and the implications of an unexpected pregnancy. Investigators shall advise WOCBP and male subjects who are sexually active with WOCBP on the use of highly effective methods of contraception. Highly effective methods of contraception have a failure rate of < 1% when used consistently and correctly.

At a minimum, subjects must agree to the use of one method of highly effective contraception as listed below:

- Male condoms with spermicide
- Hormonal methods of contraception including combined oral contraceptive pills, vaginal ring, injectables, implants and intrauterine devices (IUDs) such as Mirena® by WOCBP subject or male subject's WOCBP partner. Female partners of male subjects participating in the study may use hormone based contraceptives as one of the acceptable methods of contraception since they will not be receiving study drug
- IUDs, such as ParaGard®
- Tubal ligation
- Vasectomy.
- Complete Abstinence*

*Complete abstinence is defined as complete avoidance of heterosexual intercourse and is an acceptable form of contraception for all study drugs. Female subjects must continue to have pregnancy tests. Acceptable alternate methods of highly effective contraception must be discussed in the event that the subject chooses to forego complete abstinence

4.2.2 Exclusion Criteria

Target Disease Exceptions

- Atrial fibrillation due to a reversible cause other than recent surgery
- Patients diagnosed with persistent or paroxysmal atrial fibrillation chronically before undergoing surgery

- Patients with mechanical heart valves

Medical History and Concurrent Diseases

- Patients currently experiencing active bleeding precluding initialization of anticoagulation therapy in the opinion of their managing physician, or with increased bleeding risk (as determined by the attending surgeon) believed to be a contraindication to anticoagulation at the time of randomization Planned major surgery requiring stoppage of anticoagulation therapy during trial period
- Stroke within the previous 7 days
- Moderate or severe mitral stenosis
- Conditions other than atrial fibrillation that required anticoagulation (prosthetic mechanical heart valve)

Concomitant Medications

-
- Patients taking warfarin, apixaban, rivaroxaban, dabigatran, edoxaban, or enoxaparin at home for any indication in the 15 days prior to surgery. Patients taking clopidogrel or ticagrelor within 5 days prior to surgery, patients taking prasugrel within 7 days prior to surgery, and patients taking ticlopidine within 10 days prior to surgery
- Patients receiving clopidogrel, ticagrelor, prasugrel, or ticlopidine during the study period

Physical and Laboratory Test Findings

- Severe renal insufficiency (serum creatinine level of >2.5 mg/dL or CrCL<25 ml/min) for consecutive measurements

Allergies and Adverse Drug Reactions

- Allergies to warfarin or apixaban, or components of warfarin or apixaban

Sex and Reproductive Status

- *See Section on WOCBP above (Section 4.2.1, item # 3.)*

Other Exclusion Criteria

- Prisoners or subjects who are involuntarily incarcerated.
- Subjects who are compulsorily detained for treatment of either a psychiatric or physical (eg, infectious disease) illness.
- Patients <18 years of age.
- Patients unable to give informed consent.

Eligibility criteria for this study have been carefully considered to ensure the safety of the study subjects and to ensure that the results of the study can be used. It is imperative that subjects fully meet all eligibility criteria.

4.2.3 Women of Childbearing Potential

A Women of childbearing potential (WOCBP) is defined as any female who has experienced menarche and who has not undergone surgical sterilization (hysterectomy or bilateral oophorectomy) and is not postmenopausal. Menopause is defined as 12 months of amenorrhea in a woman over age 45 years in the absence of other biological or physiological causes. In addition, females under the age of 55 years must have a serum follicle stimulating hormone, (FSH) level > 40mIU/mL to confirm menopause.

*Females treated with hormone replacement therapy, (HRT) are likely to have artificially suppressed FSH levels and may require a washout period in order to obtain a physiologic FSH level. The duration of the washout period is a function of the type of HRT used. The duration of the washout period below are suggested guidelines and the investigators should use their judgement in checking serum FSH levels. If the serum FSH level is >40 mIU/ml at any time during the washout period, the woman can be considered postmenopausal :

- 1 week minimum for vaginal hormonal products (rings, creams, gels)
- 4 week minimum for transdermal products
- 8 week minimum for oral products

Other parenteral products may require washout periods as long as 6 months.

4.2.4 Discontinuation of Subjects from Treatment

Subjects MUST discontinue investigational product (and non-investigational product at the discretion of the investigator) for any of the following reasons:

- Withdrawal of informed consent (subject's decision to withdraw for any reason).
- Any clinical adverse event, laboratory abnormality, or intercurrent illness which, in the opinion of the investigator, indicates that continued participation in the study is not in the best interest of the subject.
- Pregnancy
 - Instruct WOCBP to contact the investigator or study staff immediately if they suspect they might be pregnant (eg, missed or late menstrual period) at any time during study participation. Institutional policy and local regulations should determine the frequency of on-study pregnancy tests for WOCBP enrolled in the study.
 - The investigator must immediately notify BMS if a study subject becomes pregnant.

- Loss of ability to freely provide consent through imprisonment or involuntary incarceration for treatment of either a psychiatric or physical (eg, infectious disease) illness.
- While patients may request withdrawal from the study at any time, they will be advised to check with their medical provider before discontinuing any anticoagulant medication, for their safety.
- Subjects can voluntarily withdraw from the study at any time, but the investigators will continue to follow the patient so that an intent-to-treat analysis can be performed. Failure to take study medication as prescribed, or failure to follow up as directed with the anticoagulation clinic, will be noted in our analysis to the best extent we are able.
- Any data collected before withdrawal will be used for study outcomes, although it will be noted that the participant did not complete the 30-day course of therapy. Attempts will be made to determine and note the reason for withdrawal.
- All subjects who discontinue should comply with protocol-specified follow-up procedures outlined in Section 6. The only exception to this requirement is when a subject withdraws consent for all study procedures or loses the ability to consent freely (ie, is imprisoned or involuntarily incarcerated for the treatment of either a psychiatric or physical illness). If a subject withdraws before completing the study, the reason for withdrawal must be documented appropriately.

5 TREATMENTS

5.1 Study Treatment: Apixaban

Definition of Investigational Product: A pharmaceutical form of an active substance or placebo being tested or used as a reference in a clinical study, including products already with a marketing authorization but used or assembled (formulated or packaged) in a way different from the authorized form, or used for an unauthorized indication, or when used to gain further information about the authorized form. In this protocol, the investigational product is apixaban. The control (current standard of care) is warfarin.

Definition of Non-Investigational Product: Other medications used in the study as support or escape medication for preventative, diagnostic, or therapeutic reasons as components of a given standard of care. In this protocol, the non-investigational products are: none.

5.1.1 Identification

Product Description / Class and Dosage Form	Potency	Blinded or Open Label	Packaging/ Appearance
Apixaban	5mg	Open	Pink, oval, biconvex Debossed with “894” on one side and “5” on the other side
Apixaban	2.5mg	Open	Yellow, round, biconvex Debossed with “893” on one side and “2½” on the other side
Warfarin	1mg 2mg, 2.5mg, 3mg, 4mg, 5mg, 6mg, 7.5mg, 10mg	Open	All strengths are tablets. 1mg: pink, 2mg: lavender, 2.5mg: light green, 3mg: tan, 4mg: blue, 5mg: peach, 6mg: teal, 7.5mg: yellow, 10mg: white

Medication storage:

Apixaban: Store at 20°C to 25°C (68°F-77°F); excursions permitted between 15°C and 30°C (59°F-86°F). Protect from light and moisture.

Warfarin: Store at controlled room temperature, (59°-86°F, 15°-30°C). Protect from light and moisture.

5.1.2 Handling and Dispensing

The investigational product should be stored in a secure area according to local regulations. The investigator is responsible for ensuring that it is dispensed only to study subjects and only from official study sites by authorized personnel, as dictated by local regulations.

If concerns regarding the quality or appearance of the investigational product arise, do not dispense the investigational product, and contact BMS immediately.

5.1.3 Drug Destruction

Ensure that arrangements have been made for investigational drug disposal, and that procedures for proper disposal have been established according to applicable regulations, guidelines, and institutional procedures.

5.2 Drug Ordering and Accountability

5.2.1 Initial Orders

Following submission and approval of the required regulatory documents, a supply of STUDY DRUG (apixaban) may be ordered through the BMS protocol manager by completing a Drug Request Form. The first request will take place upon site opening.

5.2.2 Re-Supply

Drug re-supply request form should be submitted electronically or by fax to the BMS protocol manager at least ten business days before the expected delivery date.

5.2.3 Accountability

Investigational product documentation must be maintained that includes all processes required to ensure drug is accurately administered. This includes documentation of drug storage, administration and, as applicable, storage temperatures, reconstitution, and use of required processes (eg, required diluents, administration sets).

5.3 Method of Assigning Subjects to a Treatment

Patients will be randomized to a treatment arm (apixaban or warfarin) in a 1:1 ratio by utilizing a random permuted block method, using blocks of four to eight, which was randomly generated. This ensures that with every four, six, or eight patients randomized, an equal number of subjects will be in each treatment arm, without the possibility of study personnel knowing or predicting the next randomization event.

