9	STATISTICAL CONSIDERATIONS.....	38
9.1	Sample Size DeterminationError! Bookmark not defined.	36
9.2	Populations for Analyses	38
9.3	Analyses	36
10	STUDY MANAGEMENT	39
10.1	Compliance with the Protocol.....	39
10.2	Records Retention	40
10.2.1	Records Retention	40
10.2.2	Study Drug Records.....	40
10.3	Destruction of Investigational Product.....	41
11	GLOSSARY OF TERMS.....	42
12	LIST OF ABBREVIATIONS	43
13	REFERENCES.....	44

PROTOCOL SYNOPSIS

Protocol Title:	Apixaban versus warfarin for the management of post-operative atrial fibrillation: a prospective, controlled, randomized pilot study
Site Numbers & Names:	Sanford Medical Center, Fargo, ND
Research Hypothesis:	We hypothesize that there will be no significant differences between apixaban and warfarin anticoagulation strategies for the outcomes of venous thromboembolism/stroke or bleeding events when utilized for new-onset postoperative atrial fibrillation after isolated coronary artery bypass grafting (CABG).
Study Schema: Drugs / Doses / Length of Treatment)	
Patients who develop persistent atrial fibrillation after isolated coronary artery bypass grafting will be identified and randomized to anticoagulation with either warfarin (standard of care) or apixaban.
 
Warfarin will be dosed daily, with International Normalized Ratio (INR) monitoring per hospital protocol. After discharge, warfarin dosing will be managed by the anticoagulation clinic per protocol with a target INR of 2-3.
 
Apixaban will be dosed at 5 mg twice daily, or 2.5 mg twice daily in patients with at least two of the following characteristics: age \geq 80 years, weight \leq 60 kg, or serum creatinine \geq 1.5 mg/dL.
 
Patients will remain on anticoagulation until no longer needed (typically within 30 days of surgery). Study follow-up will be through the patient's 30-day follow-up appointment.

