Study Objectives:	
1) Primary endpoint: freedom from stroke or thromboembolic event will be captured.
 
2) Secondary endpoints: -units of blood given after initiation of anticoagulation medication -total post-operative length of stay -duration from diagnosis of post-operative atrial fibrillation (POAF) to discharge from hospital -time in therapeutic range of INR if on warfarin -patient compliance percentage to apixaban if on apixaban
 
3) Safety assessments: major and minor bleeding events, as defined by the International Society on Thrombosis and Haemostasis, will be captured. Clinical events and blood product utilization will be identified and captured.

Study Design:	
In this open-label, prospective, randomized pilot study, patients who develop atrial fibrillation after isolated coronary artery bypass grafting surgery will be identified. Patients with persistent atrial fibrillation (>12 hours) or recurrent sustained atrial fibrillation (≥ 2 episodes of atrial fibrillation lasting longer than 30 minutes) will be candidates for inclusion. Upon meeting study inclusion and exclusion criteria, and after informed consent, patients will be randomized to either the standard of care (warfarin per protocol) or apixaban arms of the trial. Routine postoperative care after CABG will occur in both groups. Upon discharge, anticoagulation in both groups will be managed by the anticoagulation clinic. Patients will be followed for 30 days after surgery.

Accrual Goal: (Total number of subjects)	56 patients
Accrual Rate: (Number of subjects expected per month)	We anticipate enrolling 2-3 patients per month based on current projections.
FPFV: LPFV: Follow Up: (mm/dd/yy)	FPFV: 9/1/16 LPFV: 12/31/18 Follow up: 30 days per patient Final Report: 3/31/19

Correlative Studies: (PK/PD, etc.)
	
Retrospective analysis conducted at our facility:
 
Anderson E, Johnke K, Leedahl D, Dyke, C. Novel oral anticoagulants vs warfarin for the management of postoperative atrial fibrillation: clinical outcomes and cost analysis. American Journal of Surgery. Volume 210, Issue 6, 1095-1103²

Inclusion Criteria:
	
Patients diagnosed with new-onset persistent or recurrent atrial fibrillation after isolated CABG surgery. Persistent atrial fibrillation is defined as an episode of >12 hours. Recurrent atrial fibrillation is defined as 2 or more episodes of atrial fibrillation lasting longer than 30 minutes.

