5.5 Blinding/Unblinding

Not applicable; study is unblinded.

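### Section 5.3 says the next allocation cannot be predicted; with permuted blocks of 4, 6 or 8 in an open-label trial at one site it partly can, and no concealed release is described.

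*Combined protocol and SAP*

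**What the plan says.** Section 5.3 allocates patients "in a 1:1 ratio by utilizing a random permuted block method", "using blocks of four to eight, which was randomly generated". It then names the balance points: "with every four, six, or eight patients randomized, an equal number of subjects will be in each treatment arm". The same sentence ends by saying that this is achieved "without the possibility of study personnel knowing or predicting the next randomization event".

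The synopsis lists one site, "Sanford Medical Center, Fargo, ND", and describes the trial as open-label. Section 5.5 on blinding reads "Not applicable; study is unblinded". No stratification is stated, so there is a single allocation sequence.

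Section 4.2.2 (and the synopsis) excludes patients with "increased bleeding risk (as determined by the attending surgeon) believed to be a contraindication to anticoagulation at the time of randomization". In the Time and Events Schedule (section 6.1), consent, eligibility review and randomization all fall in the column after diagnosis of atrial fibrillation, with no stated order among them. The documents do not say who holds the list, or how an allocation is hidden until a patient is committed to the trial.

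**The concern.** Forced balance within a block is what makes the later allocations in that block predictable, so the balance promised in section 5.3 and the unpredictability claimed beside it conflict. In an open-label trial at one site, staff can see every past allocation, and the protocol tells them the possible block lengths.

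This matters because someone must judge bleeding risk at the time of randomization. If the likely next arm is foreseen, that judgement, or the decision to approach a patient for consent, could lean with it. The outcomes most exposed are bleeding, transfusion and length of stay. The blinded adjudication covers thromboembolism and stroke only, and it protects the assessment of events, not the choice of who enters. An intent-to-treat analysis cannot undo selection that happens before randomization.

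**Working it through.** Section 5.3 gives no figure for predictability, so there is none to reproduce. Its claim amounts to 50% correct guesses and no certain calls.

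**Inputs.** 56 patients, 28 per arm (sections 4.1 and 9.1); 1:1 allocation with block sizes 4, 6 and 8 (section 5.3); past allocations visible (synopsis and section 5.5). The protocol does not give the probability of each block size. I assume they are equally likely and show the range.

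**Step 1: guessing the arm that is behind.** This needs no knowledge of block sizes. For a fixed block of 2m, the expected number of correct guesses is m + 2^(2m−1)/C(2m, m) − 1/2.

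- Size 4: 2 + 8/6 − 0.5 = 2.833, and 2.833/4 = 70.8%.
- Size 6: 3 + 32/20 − 0.5 = 4.1, and 4.1/6 = 68.3%.
- Size 8: 4 + 128/70 − 0.5 = 5.329, and 5.329/8 = 66.6%.
- Equal mix: (2.833 + 4.1 + 5.329)/(4 + 6 + 8) = 12.262/18 = 68.1%.

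A real list stops at 56, often inside a block, which lowers this slightly. Simulating 20,000 lists of 56 gives 67.7%.

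**Step 2: a guesser who also knows the sizes.** Such a person can update the probability of each block size and position after every allocation. The same simulation gives 67.8% correct, or 0.678 × 56 = about 38 correct calls against 28 by chance, about 10 extra. Knowing the sizes barely changes this figure.

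**Step 3: how certain the calls are.** Two cases at the start of the list can be checked by hand.

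- Three identical allocations rule out a block of 4. Their probability is 2/20 = 0.100 in a block of 6 and 2 × (4×3×2)/(8×7×6) = 0.143 in a block of 8. The next is then the other arm with probability (0.100 × 1 + 0.143 × 4/5)/(0.100 + 0.143) = 88%.
- Four identical allocations can occur only in a block of 8, so the next four are known. This case alone disproves the absolute claim.

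Simulation over the whole list:

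| Guesser | Correct | At least 80% certain | Fully certain, per trial |
|---|---|---|---|
| Knows 4, 6, 8, equally likely | 67.8% | 23% (0.23 × 56 = about 13) | 1.3 |
| Knows the sizes and an unequal mix (60% on one size) | within the fixed-size limits, 66.6% to 70.8% | 20% to 33% | 0.8 to 2.1 |
| Sizes withheld, allows for 2 to 12 | 67.7% | about 4% (0.04 × 56 = about 2) | 0 |

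In the first row, 38% of simulated trials contain at least one fully certain allocation.

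**The case against.** Mixing block sizes is the usual safeguard against prediction, and here it works to a degree. Fixed blocks would give roughly 11 to 19 certain allocations per trial. The mixed scheme gives about 1.3, and 62% of simulated trials (100% − 38%) have none. That stands, and it limits the size of the problem.

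The route to bias is also narrow. The bleeding-risk exclusion concerns anticoagulation in general, so it applies to both arms. Nothing shows that the surgeon keeps a tally. With about two enrolments a month among inpatients, holding a patient back for a better slot would in practice mean excluding that patient. Section 9.1 enrols the first 56 who meet the criteria, and the synopsis concedes that the trial is not powered to compare events. These points limit the room for selection but do not remove it: the judgement stays discretionary, and section 9.1 intends the results as a reference for future studies.

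A reader might infer that the printed sizes cause the 68%. They do not, since it is unchanged when the sizes are withheld. A reader might also infer that randomization no longer protects the comparisons, or that patients were selectively entered. The documents show an opportunity and nothing more, and no bias in any endpoint can be estimated from them.

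**Conclusion.** The statement in section 5.3 is wrong as written and should be corrected. About 68% of allocations can be guessed, which is a property of small blocks with visible past allocations. The part the sponsor can cheaply remove is the high-certainty calls: about 23% of allocations at least 80% certain and about 1.3 fully certain per trial, against about 4% and none when the sizes are unknown. Together with a discretionary exclusion and no described concealment, this leaves some room for selection bias in the bleeding, transfusion and stay comparisons.

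The figures rest on three assumptions: equally likely block sizes (20% to 33% and 0.8 to 2.1 under unequal mixes), a guesser who follows the whole sequence, and, for the withheld case, one who allows for sizes from 2 to 12. The finding does not establish that the block scheme must be replaced.

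**What to change.** - Delete the absolute claim from section 5.3, and acknowledge that some predictability remains in an open-label blocked trial.
- Move the block sizes to a restricted randomization document not available to recruiting staff. The gain is smaller for anyone who has already read them.
- Name a person or function outside recruitment to hold the list and release each allocation only after consent and eligibility, including the surgeon's bleeding-risk judgement, are recorded. This stops a decision being reversed once the arm is seen. It does not stop a guess made beforehand, which is why the acknowledgement is needed.

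The cost is an edit to section 5.3, a short restricted document and a release step. No release system is described, so one must be named or set up. Sample size, treatments and endpoints do not change. Changing the randomization scheme is optional and not part of this fix.
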